## 11.2 Secondary Efficacy Analyses

The secondary efficacy endpoints are plasma glucose recovery within 10, 15, 20 and 30 minutes after trial product injection, ie, achieving a  $\geq 20$  mg/dL increase in plasma glucose from baseline at 0 to 10, 15, 20, and 30 minutes.

Actual timepoints of sampling will be used for this calculation.

If a patient has received an IV glucose treatment before recovery, the patient is set to “not recovered” in the analysis of the 4 endpoints, corresponding to censoring in the time-to-recovery analysis for the primary endpoint. The 10-, 15-, 20-, and 30-minute recovery rates of dasiglucagon and Placebo will be compared by a Cochran-Mantel-Haenszel test stratified by age group and injection site. The treatment responder rates with the 95% confidence intervals will be presented for the 10-, 15-, 20-, and 30-minute endpoints.

If due to small or zero cell counts the Cochran-Mantel-Haenszel test fails, non-stratified Fisher exact tests will be applied instead.

Plasma glucose changes from baseline at 10, 15, 20, and 30 minutes after trial product injection will be analyzed in an analysis of variance with factors treatment (3 levels), age group (2 levels), and injection site (2 levels) for each endpoint. If the rescue IV glucose was administered before 10, 15, 20, or 30 minutes, respectively, the patient’s plasma glucose changes from baseline will be determined from the value at the time of rescue IV glucose administration.

The change from baseline is calculated using the nominal sampling time.

Least-square mean adjusted treatment means will be presented with their 95% confidence intervals including the 95% confidence intervals for the treatment difference. The analysis of variance at each of the 4 time points will also be used to test the difference of dasiglucagon and Placebo adjusted for age group and injection site.

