2. Clinically significant illness within 4 weeks before dosing, as judged by the investigator
3. Consumption of alcohol within 24 hours prior to dosing visit, determined by positive results from an alcohol breath test
4. Not fasting from 22:00 hours the evening prior to dosing, apart from water.
5. The use of any non-prescribed systemic or topical medication, except routine vitamins and occasional use (as judged by the investigator) of acetylsalicylic acid and paracetamol within 2 weeks prior to dosing. Treatment with insulin, including analogs, is allowed
6. Use of insulin degludec or insulin glargine U300 within 72 hours prior to dosing; or use of other long-acting insulins (e.g. insulin glargine U100 or insulin detemir) within 48 hours prior to dosing; or use of neutral protamine Hagedorn insulin NPH within 22 hours prior to dosing
7. Use of any short acting (bolus) insulin within 12 hours prior to dosing, except insulin glulisine (Apidra®)
8. Changes in medical history or concomitant medication resulting in fulfillment of clinical exclusion criteria, as judged by the investigator
Plasma glucose value <50 mg/dL (2.8 mmol/L) within the last 24 hours or plasma glucose value <60 mg/dL (3.3 mmol/L) within the last 5 hours prior to admission to the clinic.

Test product, dose and mode of administration:

Dasiglucagon, liquid formulation, 1 mg/mL, 0.6 mL

Reference product, dose and mode of administration:

Placebo for dasiglucagon (hereafter referred to as placebo): Placebo, liquid formulation, 0.6 mL

Active control: Recombinant glucagon hydrochloride, 1 mg lyophilized powder for reconstitution (GlucaGen®, Novo Nordisk) in 1 mL sterile water (hereafter referred to as GlucaGen®). In accordance with the label, children below 25 kg body weight will be administered 0.5 mg GlucaGen®

Duration of treatment:

Patients will receive a single subcutaneous dose of investigational product. Patients will be subjected to a hypoglycemic clamp procedure and have to be within a plasma glucose target range of 54-80 mg/dL at dosing. The total individual trial duration will be a maximum of 63 days (up to 30 days screening, 1 dosing, 28 [+5] days of follow-up).

Criteria for evaluation:

Primary endpoint

Time to plasma glucose recovery. Plasma glucose recovery is defined as first increase in plasma glucose of ≥20 mg/dL (1.1 mmol/L) from baseline during the hypoglycemic clamp procedure without administration of rescue intravenous (IV) glucose.

Secondary endpoints

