## 10.7 Multiple Comparison/Multiplicity

For the confirmatory analyses of the primary and secondary endpoints, patients treated with either dasiglucagon 0.6 mg and or placebo will be compared. A hierarchical procedure will be applied for the control of multiplicity. The primary and secondary endpoints will be evaluated on the FAS.

For the confirmatory analyses, the following a priori-defined hierarchical inferential test order will be applied for the control of the type 1 error rate across the planned multiple comparisons. The primary endpoint and secondary endpoints will be inferentially evaluated within the FAS in the following order, where inference will proceed at the 2-sided 0.05 criterion significance level until the first failure to reject the null hypothesis for a dasiglucagon versus placebo comparison:

- Primary: Time to plasma glucose recovery
- Secondary 1-4: Plasma glucose recovery within 30 minutes, within 20 minutes, within 15 minutes, and within 10 minutes after study drug injection without administration of rescue IV glucose.
- Secondary 5-8: Plasma glucose changes from baseline at 30 minutes, at 20 minutes, at 15 minutes, and at 10 minutes after study drug injection or at the time of rescue.

The GlucaGen® versus placebo comparisons will not be included in the inferential testing hierarchy, since the efficacy of GlucaGen® is previously established, and these comparisons are intended to support the validity of the study for the dasiglucagon versus placebo comparisons. Moreover, the comparison of dasiglucagon versus GlucaGen® is not part of this hierarchical testing procedure.

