The primary endpoint will additionally be analyzed using a discrete-time Cox proportional hazards (CPH) time to event statistical model, if the hazards by treatment group can be assumed

proportional using a graphical comparison of log-minus-log survival curves and no more than two-thirds of the recovery times are censored in each treatment group. The CPH model will be used for descriptive purposes, with treatment group, age group and injection site modeled as categorical effects, and baseline plasma glucose modelled as a continuous covariate. The treatment group hazard ratios of active versus placebo, will be estimated together with the 95% confidence intervals, and pairwise treatment group inferences (dasiglucagon vs placebo, GlucaGen vs placebo, dasiglucagon vs GlucaGen) will be evaluated using least-square mean and standard deviation estimates.

Due to the discrete nature of blood sampling in time, and the fact that there must be a true, but unmeasured, ordering of the recovery times, the method using the “exact discrete” partial likelihood for tied failure times will be applied. In SAS, this is implemented in the `phreg` procedure with the option `ties=discrete`. The influence of age and injection site on time to recovery will also be evaluated in the proportional hazards model by a ‘type 3’ test in the `phreg` procedure.

In addition, separate CPH models will be calculated to evaluate homogeneity for the following factors:

Sex, BMI class, ethnicity, race, US/non-US.

These additional homogeneity models are only presented for the primary efficacy analysis, but not for subsequent variants of that analysis.

To obtain an estimate of these true, but unassessed, patient recovery times, a linear interpolation (between the two time points before and after recovery is observed) will be carried out to estimate the patients’ actual time of recovery. These derived recovery times will be described and analysed in the same manner as for the discrete times above.

Let  $t_1$  and  $t_2$  be the 2 time points before and after recovery is observed and  $y_1$  and  $y_2$  be the corresponding changes from baseline in glucose concentrations, where  $y_1$  is below 20 mg/dL and  $y_2$  is greater than 20 mg/dL.

The interpolated time point  $t_{ext}$  is calculated then as:

$$t_{ext} = t_1 + \frac{(20 - y_1) * (t_2 - t_1)}{(y_2 - y_1)}$$

This linear interpolation is only used as a supportive analysis to the primary analysis model using `proc lifetest`.

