14.2.1.11	Time to plasma glucose recovery – using linear interpolation of the time to recovery – Kaplan Meier survival curve	FAS	
14.2.2	Secondary efficacy endpoints		
14.2.2.1	Plasma glucose recovery within 10, 15, 20 and 30 minutes after trial product injection	FAS	Including p-values from CMH or Fisher’s exact test and 95% CIs for response rates of each treatment group
14.2.2.2	Plasma glucose - untransformed results at 10, 15, 20 and 30 minutes after trial product injection	FAS	
14.2.2.3	Plasma glucose - change from baseline results and inferential test statistics at 10, 15, 20 and 30 minutes after trial product injection	FAS	Results from ANCOVA will be displayed here
14.3	Safety data		
14.3.1	Displays of Adverse Events		
14.3.1.1	Overall summary of adverse events	Safety analysis set	
14.3.1.2	TEAEs by system organ class and preferred term	Safety analysis set	
14.3.1.3	TEAEs of special interest by system organ class and preferred term	Safety analysis set	
14.3.1.4	Other important TEAEs by system organ class and preferred term	Safety analysis set	

Table Number	Table Title	Analysis Set	Comment
14.3.1.5	TEAEs, which are injection site reactions	Safety analysis set	
14.3.1.6	Study drug-related TEAEs by system organ class and preferred term	Safety analysis set	
14.3.1.7	TEAEs by system organ class and preferred term and causal relationship	Safety analysis set	
14.3.1.8	TEAEs by system organ class and preferred term and severity	Safety analysis set	
14.3.1.9	SAEs by system organ class and preferred term	Safety analysis set	
14.3.1.10	Special search category TEAEs	Safety analysis set	
14.3.2	Listings of deaths, other serious and significant adverse events		This is a cross-reference to listing 16.2.7.4
14.3.3	Narratives of deaths, other serious and certain other significant adverse events		This is a cross-reference to section 12.3.2 of the CSR
14.3.4	Extent of exposure		
14.3.4.1	Insulin administration prior to the hypoglycemia induction procedure	Safety analysis set	
14.3.4.2	Hypoglycemia induction procedure	Safety analysis set	
14.3.4.3	Trial medication	Safety analysis set	
14.3.4.4	Post-treatment rescue glucose infusion	Safety analysis set	
14.3.5	Other safety data		
14.3.5.1	ECG		

Table Number	Table Title	Analysis Set	Comment
14.3.5.1.1	ECG, overall interpretation	Safety analysis set	
14.3.5.1.2	ECG, descriptive statistics of all ECG parameters	Safety analysis set	

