	20 min after dosing	Mean (SD)	xx.x (xx.xx)	xx.x (xx.xx)	xx.x (xx.xx)	xx.x (xx.xx)
		Median	xx.x	xx.x	xx.x	xx.x
		Min, Max	xx, xx	xx, xx	xx, xx	xx, xx
	30 min after dosing	n	xx	xx	xx	xx
		Mean (SD)	xx.x (xx.xx)	xx.x (xx.xx)	xx.x (xx.xx)	xx.x (xx.xx)
		Median	xx.x	xx.x	xx.x	xx.x
	Min, Max	xx, xx	xx, xx	xx, xx	xx, xx	

If the rescue IV glucose was administered before 10, 15, 20, or 30 minutes, respectively, the patient's plasma glucose changes from baseline is determined from the value at the time of rescue IV glucose administration.

PROGRAM SOURCE:###, DATA CUT OFF DATE: ddmmmyyyy

RUN DATE: ddmmmyyy hh:mm CET

14.2.2.2: Plasma glucose - change from baseline results and inferential test statistics at 10, 15, 20 and 30 minutes after trial product injection

Variable	Time Point						p-value  (95% CI) dasiglucagon versus Placebo
			dasiglucagon (N=xxx)	Placebo (N=xxx)	GlucaGen (N=xxx)	Total (N=xxx)	
Change from Baseline	10 min after dosing	n	xx	xx	xx	xx	
		Mean (SD)	xx.x (xx.xx)	xx.x (xx.xx)	xx.x (xx.xx)	xx.x (xx.xx)	
		Median	xx.x	xx.x	xx.x	xx.x	
		Min, Max	xx, xx	xx, xx	xx, xx	xx, xx	x.xxxx
		LS-mean	xx.xx	xx.xx	xx.xx	xx.xx	xx.xx
		95%CI (LS-mean)	[xx.x; xx.x]	[xx.x; xx.x]	[xx.x; xx.x]	[xx.x; xx.x]	[xx.x; xx.x]
	15 min after dosing	N	xx	xx	xx	xx	
		Mean (SD)	xx.x (xx.xx)	xx.x (xx.xx)	xx.x (xx.xx)	xx.x (xx.xx)	
		Median	xx.x	xx.x	xx.x	xx.x	
		Min, Max	xx, xx	xx, xx	xx, xx	xx, xx	x.xxxx
		LS-mean	xx.xx	xx.xx	xx.xx	xx.xx	xx.xx
		95%CI (LS-mean)	[xx.x; xx.x]	[xx.x; xx.x]	[xx.x; xx.x]	[xx.x; xx.x]	[xx.x; xx.x]
	20 min after dosing	n	xx	xx	xx	xx	
		Mean (SD)	xx.x (xx.xx)	xx.x (xx.xx)	xx.x (xx.xx)	xx.x (xx.xx)	
		Median	xx.x	xx.x	xx.x	xx.x	
		Min, Max	xx, xx	xx, xx	xx, xx	xx, xx	x.xxxx
		LS-mean	xx.xx	xx.xx	xx.xx	xx.xx	xx.xx
		95%CI (LS-mean)	[xx.x; xx.x]	[xx.x; xx.x]	[xx.x; xx.x]	[xx.x; xx.x]	[xx.x; xx.x]
	30 min after dosing	n	xx	xx	xx	xx	
		Mean (SD)	xx.x (xx.xx)	xx.x (xx.xx)	xx.x (xx.xx)	xx.x (xx.xx)	
		Median	xx.x	xx.x	xx.x	xx.x	
Min, Max		xx, xx	xx, xx	xx, xx	xx, xx	x.xxxx	
LS-mean		xx.xx	xx.xx	xx.xx	xx.xx	xx.xx	
95%CI (LS-mean)		[xx.x; xx.x]	[xx.x; xx.x]	[xx.x; xx.x]	[xx.x; xx.x]	[xx.x; xx.x]	

If the rescue IV glucose was administered before 10, 15, 20, or 30 minutes, respectively, the patient's plasma glucose changes from baseline is determined from the value at the time of rescue IV glucose administration.

 p-values calculated using an analysis of variance (ANOVA) with factors treatment, age group and injection site

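### The four confirmatory glucose-change tests omit baseline glucose from the model, and the SAP calls that model ANOVA in two places and ANCOVA in a third

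*SAP*

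**What the plan says.** SAP 10.7 puts these endpoints in the fixed testing sequence: "Secondary 5-8: Plasma glucose changes from baseline at 30 minutes, at 20 minutes, at 15 minutes, and at 10 minutes after study drug injection". In that sequence "inference will proceed at the 2-sided 0.05 criterion significance level until the first failure to reject the null hypothesis". They are therefore confirmatory comparisons of dasiglucagon with placebo.

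The model appears in three places in the SAP:

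- **Section 11.2:** the changes are "analyzed in an analysis of variance with factors treatment (3 levels), age group (2 levels), and injection site (2 levels) for each endpoint", and the model is used to "test the difference of dasiglucagon and Placebo adjusted for age group and injection site".
- **Appendix D, footnote of the change-from-baseline layout:** "p-values calculated using an analysis of variance (ANOVA) with factors treatment, age group and injection site".
- **Appendix C, comment for Table 14.2.2.3 (the same output):** "Results from ANCOVA will be displayed here". No covariate is named.

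Protocol 10.1.3.3 has the same ANOVA as SAP 11.2. SAP Section 15, which lists departures from the protocol, does not mention a change of model for these endpoints.

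Baseline is available. SAP 10.2 defines it as the last value before dosing, and the protocol synopsis requires patients to be "within a plasma glucose target range of 54-80 mg/dL at dosing" (section 7.4.5.2.2 makes the upper limit strictly below 80). For the primary endpoint, the supportive Cox model in SAP 11.1 has treatment, age group and injection site as effects "and baseline plasma glucose modelled as a continuous covariate".

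**The concern.** A change from baseline is compared between arms without adjusting for the value it is computed from. Change is usually negatively related to baseline, through measurement error and regression to the mean. Two features of this trial add to that expectation:

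- **Rescue handling.** Under Protocol 7.4.5.2.3, one trigger for IV glucose is an absolute level, below 54 mg/dL between 8 and 44 minutes. SAP 11.2 then takes the change from the value at rescue. For a patient rescued on this trigger, the recorded change is roughly 54 minus baseline: about -1 from a start of 55 and about -25 from a start of 79. Rescue for symptoms need not follow this pattern.
- **No balancing on baseline.** Randomization is stratified by age group and injection site only, and Protocol 7.5.2 places it before the hypoglycemia procedure. The pre-dose glucose value is unknown at allocation, so with 10 placebo patients only chance balances it.

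What is at stake is the precision of four confirmatory estimates and the clarity of the prespecification. ANOVA and an ANCOVA with baseline would generally give different p-values and intervals for one table, and the SAP uses both names.

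**Working it through.** **Stated figure.** The only power figure in the plan is 90% for the primary log-rank test (SAP 5): exponential medians of 10 and 50 minutes, 20 versus 10 patients, 45 minutes' follow-up, two-sided 5%. A Lakatos calculation on these inputs gives 90.03%, which reproduces it. No power or variance is stated for endpoints 5-8, so what follows is a range under assumptions.

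**Inputs from the documents**

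- 20 dasiglucagon, 10 placebo and 10 GlucaGen patients (Protocol 10.2, SAP 5)
- Baseline window from 54 to below 80 mg/dL (Protocol 7.4.5.2.2)
- Two-sided 5% level (SAP 10.7)

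**Assumed, because the documents do not give them**

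- Baseline SD of 5 to 7.5 mg/dL. The upper value is a uniform spread over the window: 26/√12 = 7.5.
- SD of change of 10 to 25 mg/dL
- Slope of change on baseline of -0.25 to -1.0
- As a simpler alternative, a correlation r between change and baseline of 0.2 to 0.5

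**Chance imbalance in baseline, dasiglucagon minus placebo**

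SE = SD × √(1/20 + 1/10) = SD × 0.387

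| Baseline SD | SE | 1.96 × SE |
|---|---|---|
| 5 | 1.94 | ±3.8 mg/dL |
| 7.5 | 2.90 | ±5.7 mg/dL |

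**Shift in the treatment difference** = slope × imbalance. At the 1.96-SE limit it runs from 0.25 × 3.8 = 1.0 to 1.0 × 5.7 = 5.7 mg/dL.

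**Precision by correlation.** Residual variance is multiplied by 1 - r², and CI width by √(1 - r²).

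- r = 0.2: variance × 0.96, width × 0.980, a cut of 4% and 2%.
- r = 0.5: variance × 0.75, width × 0.866, a cut of 25% and 13%.

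**Precision by slope.** R² = (slope × baseline SD / SD of change)². Over the assumed grid the SE is multiplied by 0.66 to 0.999.

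Mid-case, with SD of change 15, slope -0.5 and baseline SD 7.5:

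- R² = (0.5 × 7.5 / 15)² = 0.0625
- SE multiplier √(1 - 0.0625) = 0.968
- 95% half-width 1.96 × 15 × 0.387 = 11.4 mg/dL, falling to 11.4 × 0.968 = 11.0
- Power for a 20 mg/dL difference: 93.1% without baseline, 94.5% with it

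**Size and power by simulation.** Trials of 20/10/10 were simulated 5,000 times, with baseline uniform on 54-80, slope -0.5 and residual SD 12.

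| | ANOVA | ANCOVA |
|---|---|---|
| Type I error | 4.9% | 5.3% |
| Power, 10 mg/dL difference | 50.9% | 53.5% |

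Both error rates are nominal within simulation error.

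**Degrees of freedom.** With 40 patients, the ANOVA fits 5 parameters (intercept, two for treatment, one each for age group and site), leaving 35. Adding baseline leaves 34.

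**The case against.** The strongest reply is that nothing in the planned test is invalid. In a randomized comparison, ANOVA on change scores is unbiased on average and keeps its size, as the simulation shows, and its interval already allows for chance imbalance. That stands. The point is about efficiency and a label, not bias or false positives.

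The gain may also be small. The mid-case SE falls by about 3%, and the benefit is negligible if baseline explains only a few percent of the variance of change. The SD of 7.5 is a generous upper value. Insulin stops once glucose falls below 80 mg/dL and the baseline sample is drawn 5 minutes later, so a uniform spread over the window is not established. The imbalance figures concern baseline itself; the effect on the treatment difference is that imbalance times the slope. The 20 mg/dL recovery criterion is a within-patient threshold, so it is only a loose yardstick for a between-arm difference. All of this limits the size and is accepted.

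Two further arguments concern consistency. The Cox model is descriptive, and the confirmatory log-rank, Cochran-Mantel-Haenszel and ANOVA analyses all adjust for the same two stratification factors. That is correct: the Cox model shows only that baseline was thought relevant and will be in the dataset. The ANCOVA wording is also probably a slip, since it names no covariate and both the protocol and SAP 11.2 say ANOVA. Correcting the list of tables would remove the contradiction, but would leave the precision loss.

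Finally, these endpoints come last. Under the sizing assumptions, 10-minute recovery is 50% versus 13% (1 - 2^(-10/50) = 0.129). With 20 versus 10 patients, power at that step is about 45% by Fisher's exact test and 52% by an unstratified chi-square test. On those assumptions endpoints 5-8 would be formally tested at most about half the time. That reduces the practical weight of the point, but the estimates and intervals will be reported either way.

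**Conclusion.** The concern holds. Four confirmatory comparisons of glucose change are specified without the baseline value, although it is collected before dosing and is not balanced by design. The SAP also names two different models for the same table.

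The loss is in precision and in exposure to chance imbalance. Type I error is not affected, and neither the significance level nor the planned sample size changes. The gain is 2 to 13% of CI width for an assumed correlation of 0.2 to 0.5, and about 3% in the slope-based mid-case. An imbalance at the edge of its 95% range would move the estimated difference by about 1.0 to 5.7 mg/dL under the assumed slopes. The documents fix none of these variance inputs, so the missing covariate and the conflicting labels are certain, while the size is conditional. This is a change that should be made, not one on which the trial's validity depends.

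**What to change.** In SAP 11.2, specify an ANCOVA for each of the four time points, with treatment, age group and injection site as factors and baseline plasma glucose as a continuous covariate. Change the footnote of the change-from-baseline layout in Appendix D to match, so that it agrees with the Appendix C entry for Table 14.2.2.3. Add an entry to SAP Section 15, because Protocol 10.1.3.3 prespecifies the ANOVA. Protocol 10.1 allows the SAP to adapt the planned analysis before unblinding, so this must be done before the blind is broken.

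The cost is one model term, one footnote, one line in Section 15 and one residual degree of freedom (35 to 34). No new data are needed. If the sponsor prefers to keep the ANOVA, the ANCOVA comment in Appendix C must at least be corrected so that only one model is prespecified.

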## 12. PHARMACOKINETIC ANALYSES

Plasma dasiglucagon and glucagon concentrations will be described and the following parameters are calculated and summarized with descriptive statistics:

PK parameter	PK parameter abbreviation	Calculation
Area under the plasma dasiglucagon or GlucaGen ® concentration versus time curve from 0 to 30 minutes post-dose	AUC 0-30min	Linear trapezoidal rule for the ascending part of the concentration-time curve, logarithmic trapezoidal rule for the descending part.
Area under the plasma dasiglucagon or GlucaGen ® concentration versus time curve	AUC 0-300min	Linear trapezoidal rule for the ascending part of the concentration-time curve, logarithmic trapezoidal rule for the

PK parameter	PK parameter abbreviation	Calculation
from 0 to 300 minutes post-dose		descending part.
Area under the plasma dasiglucagon or GlucaGen ® concentration versus time curve from 0 to infinitely post-dose	AUC 0-inf	(AUC last + C last,obs )/ λ z , where C last,obs is the concentration corresponding to T last (time of last measurable (positive) concentration).
Maximum of all valid plasma dasiglucagon or GlucaGen ® concentration measurements from 0 to 300 minutes post-dose	C max	Taken directly from analytical data, selected from individual concentration data. The time when the first occurrence of C max is taken as T max .
Time to maximum of plasma dasiglucagon or GlucaGen ® concentration measurements	t max	Taken directly from analytical data, selected from individual concentration data
Terminal elimination rate constant of plasma dasiglucagon or GlucaGen ®	λ z	Calculated by linear regression of the terminal linear portion of the log concentration vs. time curve. At least 3 concentrations in the terminal elimination phase will be required to calculate λ z .
Terminal plasma elimination half-life of dasiglucagon or GlucaGen ®	t 1/2	Ln(2)/ λ z
Total body clearance of plasma dasiglucagon or GlucaGen ®	CL/f	Dose/ AUC 0-inf
Volume of distribution of plasma dasiglucagon or GlucaGen ®	V z /f	Dose/ (λ z * AUC 0-inf ) or CL/f/ λ z
Mean residence time of plasma dasiglucagon or GlucaGen ®	MRT	AUMC inf / AUC 0-inf where AUMC inf is the area under the first moment curve as estimated by WinNonlin.

The PK metrics as listed above will be obtained by non-compartmental analysis using the computer programs Phoenix® WinNonlin® Version 6.4.

